4. STUDY DESCRIPTION

These following sections detail the prospective design, objectives, and sample size of Study CP 0418 SS-P2 051, Final Version 2.0 incorporating Amendment 1, dated 12-SEP-2019.

4.1 Brief Description of Study Design

Study CP 0418 SS-P2 051 "Open-Label Study of the Pharmacokinetics and Safety Including HPA Axis Suppression Potential of Clobetasol Topical Oil in Pediatric Subjects with Moderate to Severe Atopic Dermatitis" is a multicenter, single-arm, open-label study designed to evaluate the hypothalamic-pituitary-adrenal (HPA) axis suppression potential and systemic exposure to clobetasol, when administered as Clobetasol Topical Oil in pediatric subjects, under conditions consistent with anticipated clinical use and under conditions designed to maximize the potential for drug absorption in subjects with moderate to severe AD.

Up to 12 study centers in the United States will participate in the study. Up to approximately 72 subjects will be enrolled to achieve ≥ 20 completed subjects per cohort.

The study duration for each subject will be up to 54 days (up to 38 days for Screening assessments, followed by up to 16 days of treatment and follow-up). Additional time will be required for subjects requiring additional hypothalamic-pituitary-adrenal [HPA] axis function testing due to an abnormal result at End of Treatment.

The study will consist of three successively younger pediatric cohorts, as safety data allow:

- Cohort 1: ≥ 12 to < 18 years;
- Cohort 2: ≥ 6 to < 12 years; and
- Cohort 3: ≥ 2 to < 6 years.

Enrollment into each successively younger pediatric cohort will proceed only after the preceding cohort has been completed and safety and exploratory data (including adverse events [AEs], tolerability assessments, clinical laboratory results, and the percentage of subjects with HPA axis suppression) have been reviewed and agreed to be acceptable for progression to the next cohort. Enrollment into Cohorts 2 and 3 will proceed only if the percentage of subjects with HPA axis suppression in Cohorts 1 and 2, respectively, is $\leq 40\%$. HPA axis suppression is defined as a cortisol concentration $\leq 18 \mu\text{g}/100 \text{ mL}$ at approximately 30 minutes after stimulation with cosyntropin.

However, the study was terminated during enrollment of Cohort 1, after 8 subjects had been enrolled into the study. No subjects were enrolled into either of Cohorts 2 or 3.

4.2 Study Objectives

The objectives of this study are to assess the following properties of Clobetasol Topical Oil under maximal use conditions in pediatric subjects with moderate to severe AD.

- Safety, including the potential to suppress the HPA axis
- Systemic exposure to clobetasol following repeated application

4.3 Primary Objective

To assess safety, including the potential to suppress the HPA axis.

4.4 Secondary Objective(s)

To assess systemic exposure to clobetasol following repeated application.

4.5 Study Endpoints

The analysis for this study is for an abbreviated safety CSR. With the exception of safety below, all endpoints and analyses stated in the protocol have been removed and noted as changes to the planned analyses.

- Number and percentage of subjects with HPA axis suppression, defined as a post-stimulation serum cortisol concentration $\leq 18 \mu\text{g}/100 \text{ mL}$.
- Number and percentage of subjects with treatment emergent AEs (TEAEs), with TEAEs defined as those occurring after the start of study drug or increasing in intensity from Baseline to after the start of study drug.
- Clinical laboratory (chemistry and hematology) values at Screening and at the End of Treatment, presented using descriptive statistics.

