- To include burning/stinging, atrophy, striae, folliculitis, and telangiectasias.

- k. On Day 1, tolerability assessments will be performed before the first application of study drug and will constitute baseline values for each of these parameters; tolerability assessments will be performed again on Day 1 after the first application of study drug.
- l. Blood samples for determination of the clobetasol propionate plasma concentration will be collected pre-dose (this sample will be taken within 12±2 hours of the previous evening's application of study drug and within 1 hour before the application of study drug on the day of this visit), and at 1 (±10 minutes), 3 (±15 minutes), and 6 (±1 hour) hours after the application of study drug on the day of this visit.
- m. To be performed no earlier than 28 days prior to Baseline/Start of Treatment (i.e., no earlier than Day -27).

Details about study procedures and how they are to be performed are presented in Section 11.

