11.6 Tolerability Assessments

For the tolerability assessment of burning/stinging, the investigator or designee will ask the subject (or the subject's parent, guardian, or caregiver, as appropriate) to rate the subject's sensation of burning/stinging within the past 24 hours according to the scale shown in Table 3.

Table 3 Scale for Assessment of Burning/Stinging

Score	Definition
0	None; no burning or stinging
1	Mild; slight burning/stinging sensation that is not really bothersome
2	Moderate; warm, burning/stinging that is somewhat bothersome
3	Severe; hot burning/stinging sensation that causes definite discomfort and may interrupt daily activities and/or sleep

For the tolerability assessments of skin atrophy, striae, folliculitis, and telangiectasias, the investigator or designee will rate each of these parameters according to the scale shown in Table 4.

Table 4 Scale for Assessment of Skin Atrophy, Striae, Folliculitis, and Telangiectasias

Score	Definition
0	Absent
1	Present

Tolerability parameters will be reported as AEs only if they require intervention such as treatment with a medication, or interruption or discontinuation of study drug.

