12 ADVERSE EVENTS

12.1 Definition of an Adverse Event

An AE is any untoward medical occurrence in a subject or clinical investigation subject which does not necessarily have a causal relationship with the study drug. An AE can therefore be any unfavorable and unintended sign (including a clinically significant abnormal laboratory finding), symptom, or disease, whether or not considered related to the investigational or marketed study drug. AEs include any illness, sign, or symptom that has appeared or worsened during the course of the clinical trial, regardless of causal relationship to the study drug. Study drug includes the investigational drug under evaluation and any comparator product.

Medical conditions/diseases present before signing the informed consent form are only considered AEs if they worsen after the informed consent form is signed.

AEs may be either spontaneously reported or elicited during questioning and examination of a subject. At each examination or visit, study personnel will ask each subject and caregiver, as appropriate, the following question, "Have you had any problems since we last spoke?" If known, the investigator should report the diagnosis of the underlying illness or disorder, rather than its individual symptoms.

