12.2 Severity of Adverse Events

The severity of an AE will be determined by the investigator according to the following definitions:

- **Mild:** Awareness of event, but easily tolerated and does not disrupt usual activity
- **Moderate:** Sufficient to cause interference with usual activity
- **Severe:** Incapacitating, with inability to perform usual activities

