14.1.3.3 Tolerability

The following parameters will be summarized by visit:

- Number and percentage of subjects who experience each tolerability parameter (i.e., burning/stinging, skin atrophy, striae, folliculitis, and telangiectasias).

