14.4.3 Exploratory Analyses

Exploratory analyses include several measures of efficacy and tolerability. Exploratory analyses will be performed for the safety population (see Section 14.3.1) and may also be performed for one or more evaluable populations (see Section 14.3.2). Statistical summaries will be presented by visit and may be further stratified as appropriate.

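### Does dropping the tolerability table hide local skin effects that needed no intervention from the safety report?

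*SAP*

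**What the plan says.** Protocol 11.6 sets a specific reporting rule for the five tolerability parameters: "Tolerability parameters will be reported as AEs only if they require intervention". It counts treatment with a medication, and interruption or discontinuation of study drug, as intervention. Burning/stinging is graded 0 to 3. The other four parameters are scored absent or present. Protocol Table 1 schedules the assessments on Day 1, Day 8 and Day 15. On Day 1 they are made twice, and its footnote says that "tolerability assessments will be performed before the first application of study drug and will constitute baseline values for each of these parameters".

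Findings below the adverse event threshold had one planned tabulation. Protocol 14.1.3.3, under the heading Exploratory, lists by visit the "Number and percentage of subjects who experience each tolerability parameter". Protocol 14.4.3 adds: "Exploratory analyses will be performed for the safety population".

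The SAP is for an abbreviated safety report after early termination. SAP 4.5 keeps HPA axis suppression, TEAEs and laboratory values, and states: "With the exception of safety below, all endpoints and analyses stated in the protocol have been removed". SAP 3 and SAP 14 also say that exploratory analyses are dropped. SAP 6 says that data not analysed appear in listings only. SAP 16.1 has six tables, none for tolerability. SAP 16.2 has Listing 16.2.9.2, Tolerability Assessments, for the Safety population.

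**The concern.** The SAP names safety as its primary objective, and Protocol 5.1 lists all five parameters among the local risks of superpotent topical corticosteroids. Protocol 14.4.7 also reviews tolerability beside TEAEs before each cohort decision, so the protocol uses these data as safety data even though it files them as exploratory. Removing the summary by class takes away the only table in which a finding below the threshold could appear.

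Such findings need not be trivial. The top burning/stinging grade is described as "hot burning/stinging sensation that causes definite discomfort and may interrupt daily activities and/or sleep", which is close to the definition of a moderate adverse event in Protocol 12.2: "Sufficient to cause interference with usual activity". Without intervention it is still not reported as an adverse event, although the general definition in Protocol 12.1 says that "AEs include any illness, sign, or symptom that has appeared or worsened during the course of the clinical trial".

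SAP 12.1 does not repeat the Protocol 11.6 rule, and SAP 14 does not mention tolerability by name. The risk runs one way: a reader who relies on Tables 14.3.1.1 and 14.3.1.2 alone could see few skin events and conclude that there were few local effects.

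**Working it through.** No sample size, power or error rate is involved, and the plan gives no figure to reproduce. The check traces where each kind of finding goes, then sizes what is left untabulated.

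**Where each finding is reported under the SAP as written**

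| Finding | TEAE tables | Listing 16.2.9.2 |
|---|---|---|
| Starts or worsens after first dose and is treated, or leads to interruption or discontinuation of study drug | Yes (Protocol 11.6, SAP 12.1) | Yes |
| Starts or worsens after first dose, no intervention | No (Protocol 11.6) | Yes |
| Present before the first dose, unchanged | No | Yes |

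Only the middle row is at issue. It loses a summary table and loses no data.

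**What a reader is told**

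1. The adverse event rule is explicit in Protocol 11.6, and SAP 3 encourages the reader to consult the protocol.
2. The removal of exploratory analyses is stated in SAP 3 and SAP 14. Protocol 14.1.3 and 14.4.3 place tolerability in that class, so the class name covers it. ISGA and BSA are dropped in the same way and are not named in SAP 14 either.
3. The place where the data can be found follows from SAP 6 (listings only) and SAP 16.2 (a listing titled for tolerability).
4. Whether the TEAE tables will carry a footnote cannot be determined. SAP 16.1 gives table numbers, titles and populations, and the documents contain no table shells.

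**Size of the untabulated material**

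Inputs: 5 parameters (Protocol 14.1.3.3); 4 assessments, of which 3 are post-dose (Day 1 after dosing, Day 8, Day 15; Protocol Table 1); 8 children enrolled (SAP 4.6).

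- Post-dose: 5 x 3 x 8 = 120, made up of 4 x 3 x 8 = 96 skin-finding scores and 1 x 3 x 8 = 24 burning/stinging scores.
- Pre-dose baseline: 5 x 8 = 40.
- Total in the listing: 120 + 40 = 160 values.

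This assumes that all 8 children were treated and attended every visit, which the documents do not state. With 7 such children the post-dose count is 5 x 3 x 7 = 105; with 6 it is 5 x 3 x 6 = 90.

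These are scheduled assessments, not findings. A third of them (5 x 8 = 40) are Day 1 post-dose scores from the same visit as the baseline. The burning/stinging question asks about the past 24 hours, so its Day 1 post-dose score mostly covers time before treatment.

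**What a table could show, with an assumed count**

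One child of 8 is 100/8 = 12.5 percentage points. Suppose 2 of 8 children had new atrophy that needed no intervention (an assumption, not a trial result). The TEAE table would count 0/8 for atrophy, with an exact 95% upper limit of 1 - 0.025^(1/8) = 36.9%. A tolerability table would show 2/8 = 25%, with an exact 95% interval of 3.2% to 65.1%. Listing 16.2.9.2 would show both children. The two intervals overlap widely, and neither allows a firm statement about the rate.

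**The case for a change.** The strongest case for a change is that a safety report should not let low TEAE counts stand as the only summary of local effects of a superpotent steroid in children. The table is small and uses data already collected. The protocol promised it for the safety population, and Protocol 14.4.7 treats the same data as safety data. Dropping it because of the label exploratory is a decision by category, and SAP 14 could have named it.

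Part of this stands. SAP 12.1 does not carry the Protocol 11.6 rule, SAP 14 does not use the word tolerability, and someone who looked at two tables and nothing else could be misled.

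The rest does not carry the point to a change. The TEAE tables do not understate what they claim to count: they report adverse events as the protocol defines them, and the specific rule in 11.6 governs these five parameters ahead of the general wording in 12.1. Anyone who thinks 11.6 is too narrow has a question about how the protocol collected adverse events, which no SAP table can settle. The review role in 14.4.7 served a decision on opening the next cohort, and the study ended in Cohort 1. Grades for burning/stinging, or a count of findings new since baseline, would go beyond the n and percentage by visit that Protocol 14.1.3.3 planned.

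**Conclusion.** The observation about the tables is accurate, but no change to the plan follows. Leaving out the summary is a fair trade-off within a declared reduction of scope. Followed as written, the SAP gives TEAE counts that are correct under the protocol's own definition, an HPA axis result that does not depend on tolerability, and a by-subject listing of every tolerability score for at most 8 children. A listing of that length can be read in full, and an author of the report can state from it how many children had each finding.

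The most that is given up is a summary of 120 scheduled post-dose assessments (90 to 120 if 6 to 8 children were treated and fully followed). A footnote pointing to Protocol 11.6 and the listing would be a courtesy to readers, but it would alter no estimate and no conclusion.

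This rests on two conditions: that Listing 16.2.9.2 is produced for the whole Safety population, as SAP 16.2 states, and that findings leading to treatment, interruption or discontinuation were recorded as adverse events, as Protocol 11.6 requires.

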4.6 Study Sample Size

The sample size for this study (approximately 24 subjects in each of Cohorts 1, 2, and 3) was specified to provide ≥ 20 evaluable subjects within each cohort. This sample size was not based on statistical considerations and is instead intended to be a reasonable number of subjects upon which to gather both safety (including the potential to suppress the HPA axis) and systemic exposure information under maximal use conditions of Clobetasol Topical Oil in pediatric subjects.

The study was terminated during enrollment of Cohort 1, after 8 subjects had been enrolled into the study. No subjects were enrolled into either of Cohorts 2 or 3.

5. SCOPE

This SAP describes the planned statistical analyses to be performed on safety data from the Study CP 0418 SS-P2 051 "Open-Label Study of the Pharmacokinetics and Safety Including HPA Axis Suppression Potential of Clobetasol Topical Oil in Pediatric Subjects with Moderate to Severe Atopic Dermatitis".

Social & Scientific Systems, Inc. (SSS) is responsible for developing the SAP and carrying out the statistical analyses, including the production of all tables and listings.

6. GENERAL CONSIDERATIONS

All collected data will be presented in listings; no variables will be derived or computed. Data not subject to analyses according to this plan will not appear in any tables or graphics but will be included only in the data listings.

Baseline demographics will be summarized. Baseline for any given variable is defined as the observation immediately prior to application of study drug. The study Screening visit is considered baseline for laboratory and HPA axis suppression tests.

Descriptive statistics for continuous measures will include the number of subjects (n), mean, standard deviation (SD), median, 25th and 75th percentiles, and minimum (min) and maximum (max) values. Categorical and binary variables will be summarized by the frequency count (n) and percentage (%) of subjects with non-missing data per category. No imputation will be made for missing data. All analyses will be completed on the Safety population (see definition below). Additionally, HPA axis data will be summarized on the Evaluable population (see definition below).

Adverse events and medical history will be coded using the Medical Dictionary for Regulatory Activities (MedDRA) (version 22.1).

7. ANALYSIS POPULATIONS

7.1 Safety Population

The Safety population will include all enrolled subjects who received at least one application of study drug.

7.2 Evaluable Population

The Evaluable population will be defined as subjects:

- 1) who met all inclusion/exclusion criteria, and did not report use of a prohibited medication;
- 2) who during the study period used $\geq 20\%$ of study drug dispensed, based on the weight effect of the bottles, calculated as $[(\text{total (drug dispensed (g)} - \text{drug returned (g))}) / 120 \text{ g dispensed}] * 100$, as recorded on study drug accountability CRF; and
- 3) who based on data reported on the study drug missed doses CRF were compliant with the last 5 doses (including the final dose administered at the End of Treatment visit).

8. DEMOGRAPHIC AND OTHER BASELINE CHARACTERISTICS

8.1 Demographic Characteristics

Subject demographics (including age, sex, race, and ethnicity) will be summarized descriptively for the safety population and will be supported with an individual subject data listing including all enrolled subjects.

8.2 Medical History

At Screening, the investigator or designee interviewed each subject (and parents, guardians, and/or caregivers, as applicable) to obtain a complete medical and medication history, including a history of all surgeries and past medical procedures. This information was reviewed and updated at Baseline, prior to subject enrollment.

Medical history will be presented alphabetically by system organ class and preferred term. Reported terms will be coded using MedDRA version 22.1.

9. SUBJECT DISPOSITION AND PROTOCOL DEVIATIONS

A summary table will be produced detailing the number and percent of subjects enrolled, treated, who completed the study, who were at least 80% compliant with study drug, and who discontinued study participation. The primary reason for discontinuation will also be presented with the number and percentage of subjects in each category.

A listing of all subjects with one or more protocol deviations will be provided. The listing will include the protocol deviation category, visit associated with the deviation (if applicable), and a description of the deviation.

10. EFFICACY

No efficacy analyses will be performed.

11. PHARMACOKINETICS

All analyses are being conducted for an abbreviated safety CSR, and no pharmacokinetic analysis will be included in these analyses. A by-subject listing of plasma concentration levels will be produced.

12. SAFETY

The descriptive summary of safety data will be presented for the Safety population. For the summary of HPA axis function, data will be presented for both the Safety and the Evaluable populations.

12.1 Adverse Events

All AEs occurring during the study will be classified using terminology from the Medical Dictionary for Regulatory Activities (MedDRA). All AEs which start after the start of study drug or which increase from Baseline in severity will be considered treatment emergent adverse events (TEAEs). TEAEs will be summarized by number of events and number and percentage of subjects experiencing TEAEs, across all subjects. When summarizing TEAEs by severity or

relationship to study drug, each subject will be counted only once within a system organ class or a preferred term using the event with the greatest severity or causality, respectively, within each category. All reported serious AEs (SAEs) will be summarized by the number of subjects reporting the event, system organ class, preferred term, severity, and relationship to study drug.

12.2 Laboratory Evaluations

Clinical laboratory (chemistry and hematology) values at Screening and at the End of Treatment visits will be presented using descriptive statistics. Data from unscheduled visits will be included in the subject listings.

The number and percentage of subjects with HPA axis suppression, defined as a post-stimulation serum cortisol concentration $\leq 18 \mu\text{g}/100 \text{ mL}$, will be presented by visit.

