Statistical Analyses: 
The safety parameter of HPA axis suppression will be summarized at the completion of each study cohort and at the end of the study. The percentage of subjects (within cohort) who at the End of Treatment visit demonstrated a poststimulation cortisol concentration $\leq 18 \mu\text{g}/100 \text{ mL}$ will be determined and will inform subsequent cohort enrollment.
 
At the end of the study, cortisol concentrations (both before and after stimulation with cosyntropin) and the percentage of subjects with HPA axis suppression will be summarized both by cohort and across all subjects.
 
Clobetasol plasma concentrations will be summarized across subjects for each sampling time in aggregate and by cohort. PK parameters (C_{max}, T_{max}, and $\text{AUC}(0-6)$) will be calculated using non-compartmental analyses.
 
ISGA results will be summarized at each time point by the number and percentage of subjects in each ISGA category. A combined category for an ISGA score of either 0 or 1 (clear or almost clear) will also be included. In addition, the number and percentage of subjects with an improvement in ISGA score of at least 2 grades from Baseline to each post-Baseline evaluation will be determined, as will the number and percentage of subjects with an ISGA score of either 0 or 1 (clear or almost clear) and an improvement of at least 2 grades from Baseline to each post-Baseline evaluation.
 
Descriptive statistics for continuous measures will include the number of subjects (N), arithmetic and geometric mean, standard deviation (SD), median, minimum, maximum, and confidence interval (CI), where appropriate. Categorical and binary variables will be summarized by the frequency count (n) and percentage (%) of subjects with non-missing data per category.
 
No imputation will be made for missing data.
 
All AEs occurring during the study will be recorded and classified using terminology from the Medical Dictionary for Regulatory Activities (MedDRA). All AEs which start after the start of study drug or which increase from Baseline in severity will be considered treatment emergent adverse events (TEAEs). TEAEs will be summarized by number of events and number and percentage of subjects experiencing TEAEs, across all subjects and by cohort.
 
When summarizing TEAEs by severity or relationship to study drug, each subject will be counted only once within a system organ class or a preferred term using the event with the greatest severity or causality, respectively, within each category.
 
All reported serious AEs (SAEs) will be summarized by the number of subjects reporting the event, system organ class, preferred term, severity, and relationship to study drug.

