14 STATISTICAL CONSIDERATIONS

14.1 Study Endpoints

14.1.1 Safety

Safety endpoints include the following:

- Number and percentage of subjects with HPA axis suppression, defined as a poststimulation serum cortisol concentration ≤ 18 $\mu\text{g}/100$ mL, at Screening and at the End of Treatment.
- Cortisol concentrations (stratified as prestimulation and poststimulation) at Screening and at End of Treatment, presented using descriptive statistics.
- Number and percentage of subjects with treatment emergent AEs (TEAEs), with TEAEs defined as those occurring after the start of study drug or increasing in intensity from Baseline to after the start of study drug.
- Clinical laboratory (chemistry and hematology) values at Screening and at the End of Treatment, presented using descriptive statistics.
- Number and percentage of subjects with shifts from normal (within the laboratory's normal range) to abnormal (outside of the laboratory's normal range) in each clinical laboratory parameter from Screening to the End of Treatment.

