14.4.1 Safety Analyses

No subjects will be excluded from the safety population because of protocol deviations. Subjects who do not meet admission criteria prior to dosing or who have major protocol deviations after dosing that could significantly affect results will be excluded from the evaluable populations.

Cortisol concentrations, HPA axis suppression data, TEAEs, and clinical laboratory (chemistry and hematology) parameters will be summarized for the safety population (see Section 14.3.1).

TEAEs will be summarized by number of events and number and percentage of subjects experiencing TEAEs, across all subjects and by cohort. When summarizing TEAEs by severity or relationship to study drug, each subject will be counted only once within a system organ class or a preferred term using the event with the greatest severity or causality, respectively, within each category.

All reported SAEs will be summarized by the number of subjects reporting the event, system organ class, preferred term, severity, and relationship to study drug.

In addition to the safety population, cortisol concentrations and HPA axis suppression data will be summarized for the evaluable population for HPA axis function (see Section 14.3.2.1).

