14. CHANGES IN STUDY CONDUCT OR PLANNED ANALYSIS

Because the study was prematurely terminated as noted in Section 3, pharmacokinetic, exploratory, sensitivity, as well as some safety analyses will not be completed under this SAP.

Additionally, the definition of the Evaluable population (section 7.2) has been revised from the study protocol (section 14.3.2) because "planned doses" were a function of the treatable BSA and the weight of the tubing and caps biased the calculation. So, a simple 80% threshold would have excluded all of the N subjects. Therefore, compliance is computed with consideration of the weight effect of the bottles with the compliance threshold set as greater or equal to 20%.

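### The SAP specifies only a count at or below 18 µg/100 mL as its HPA axis result; the protocol's cortisol summary has no specified table and is not named among the changes

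*SAP*

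**What the plan says.** Protocol 14.1.1 lists five safety endpoints. Two concern the HPA axis and are separate items: the number and percentage with suppression, and "Cortisol concentrations (stratified as prestimulation and poststimulation) at Screening and at End of Treatment, presented using descriptive statistics". The Synopsis, under Statistical Analyses, repeats this for the final analysis: "cortisol concentrations (both before and after stimulation with cosyntropin) and the percentage of subjects with HPA axis suppression will be summarized". Protocol 14.4.1 asks for both in the safety population and then adds that "cortisol concentrations and HPA axis suppression data will be summarized for the evaluable population for HPA axis function".

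SAP 4.5 retains three safety endpoints and says of the rest that "all endpoints and analyses stated in the protocol have been removed and noted as changes to the planned analyses". The HPA item retained is the suppression count. SAP 12.2 gives the analysis: "The number and percentage of subjects with HPA axis suppression, defined as a post-stimulation serum cortisol concentration" at or below 18 µg/100 mL, by visit. SAP 12 adds "For the summary of HPA axis function, data will be presented for both the Safety and the Evaluable populations", without saying which data. SAP 16.1 lists one HPA table, 14.3.6.2, titled for suppression by visit. SAP 14 records that pharmacokinetic, exploratory and sensitivity analyses, "as well as some safety analyses will not be completed under this SAP". It does not say which safety analyses these are.

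**The concern.** SAP 4.3 makes safety, including the potential to suppress the HPA axis, the primary objective. The report has been cut down to a safety report, yet one of the two HPA safety endpoints has gone and the section meant to record changes does not name it. What remains is a yes/no count in very few children. A threshold count carries no information on how far cortisol moved, and with at most 8 children it carries little on how often suppression occurs. If the count is low or zero, the tables as specified give a reader nothing with which to judge either.

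**Working it through.** Neither document gives an interval or other figure to reproduce here. The check is a comparison of text followed by exact binomial limits.

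**1. Endpoints, protocol against SAP.**

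| Protocol 14.1.1 endpoint | Kept in SAP 4.5 | If dropped, named in SAP 14 |
|---|---|---|
| Number and percentage with HPA suppression | yes | – |
| Pre- and poststimulation cortisol, descriptive | no | no |
| TEAEs | yes | – |
| Chemistry and hematology values | yes | – |
| Normal-to-abnormal shifts "in each clinical laboratory parameter from Screening to the End of Treatment" | no | no |

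Five listed, three kept, so 5 − 3 = 2 dropped, neither of them named in SAP 14. The point here is the cortisol summary; the laboratory shifts matter only for the completeness of SAP 14.

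**2. Could another table carry cortisol?** SAP 16.1 lists six tables: disposition (14.1.1), demographics (14.1.3), adverse events (14.3.1.1 and 14.3.1.2), laboratory values (14.3.6.1) and HPA suppression (14.3.6.2). SAP 12.2 limits the laboratory summary to chemistry and hematology, and the panels in Protocol 11.8 do not include cortisol. SAP 6 sends data not analysed under the plan to listings alone. So no table is specified to show cortisol concentrations.

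**3. What the specified result contains.** Inclusion Criterion 5 (Protocol 8.1) requires stimulated cortisol above 18 at Screening. For eligible subjects the Screening row of Table 14.3.6.2 is therefore 0 by design, and all the information sits in the End of Treatment count. Hypothetical values show what that count leaves out: 18.5 to 17.8 counts the same as 30 to 6, and 30 to 19 does not count.

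**4. Uncertainty of that count.** SAP 4.1 gives 8 enrolled. The End of Treatment denominator can be smaller: percentages use non-missing data (SAP 6), and a subject who stops early is not retested if fewer than 28 days have passed since the last test (Protocol 8.4). The actual denominator is not stated, so a range is shown. For zero events the exact (Clopper-Pearson) 95% upper limit is U = 1 − 0.025^(1/n).

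- n = 8: 1 − 0.631 = 36.9%
- n = 7: 1 − 0.590 = 41.0%
- n = 6: 1 − 0.541 = 45.9%

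For 1 of 8, the lower limit is 1 − 0.975^(1/8) = 0.3%. The upper limit p solves (1 − p)^8 + 8p(1 − p)^7 = 0.025, giving 52.7%.

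**5. What restoring the protocol summary would show.** Protocol 14.1.1 asks for statistics at each visit. These would show the level and spread of cortisol before and after treatment, and so a shift in the group. They would not pick out one child who fell from 30 to 19. Only a within-subject change would summarize that, and neither document plans one.

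**The case against.** The reduction is deliberate and declared. SAP 3 explains that the study was terminated and that the report is an abbreviated one, and SAP 4.5 removes whatever it does not list. A reader who sets SAP 4.5 beside Protocol 14.1.1 can find both dropped items. SAP 6 sends all collected data to listings, and Listing 16.2.6 covers the HPA tests. With 8 children, two visits and two draws, that is at most 8 × 2 × 2 = 32 scheduled values, which can be read by eye. All of this stands, and it is why the importance is low. It does not supply the descriptive statistics that the protocol set for a safety endpoint, when chemistry and hematology summaries are kept for the same children. Nor does it make SAP 14 specific, although that section explains the changed Evaluable population in detail.

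A reader might infer more than the documents support, in three ways.

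- **That cortisol will certainly reach no table.** SAP 6 says in general terms that HPA data will be summarized for the Evaluable population, and SAP 12 speaks of HPA function. Table shells are not part of the SAP, so cortisol rows cannot be ruled out. The supported statement is that none are specified.
- **That the departure from the protocol is what hides individual falls above 18.** The protocol's own visit-level summary would not show them either.
- **That every child counted at End of Treatment was suppressed by the drug.** There is no control arm and the documents give no within-child variability, so a value that crosses 18 may be ordinary variation.

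**Conclusion.** The point holds at low importance. The specified HPA result is one End of Treatment count out of at most 8, with no measure of size or uncertainty. The protocol's cortisol summary is not specified for any table and is not named in SAP 14. Zero suppressed would be compatible with true rates of up to 36.9% (n = 8) to 45.9% (n = 6). These limits assume independent subjects and a denominator between 6 and 8. That individual values remain visible rests on the title of Listing 16.2.6 and the SAP 6 rule on listings. The 18 µg/100 mL criterion itself is not in question.

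**What to change.** 1. In Table 14.3.6.2, for the Safety and Evaluable populations, add the SAP 6 descriptive statistics (n, mean, SD, median, 25th and 75th percentiles, minimum, maximum) for pre- and poststimulation cortisol at Screening and End of Treatment. This restores Protocol 14.1.1 and 14.4.1 and needs no derived variable.
2. Put the exact 95% interval beside the count at or below 18. Neither document plans an interval for this count, so label it as an addition.
3. Optionally, add within-subject change from Screening as a labelled descriptive item (n, median, minimum, maximum). Only this summarizes individual falls that stay above 18. It needs a one-line exception to the SAP 6 sentence ruling out derived variables, a rule that is already not absolute because SAP 7.2 computes a compliance percentage.
4. In SAP 14, name each protocol safety analysis that stays dropped, including the laboratory shifts if they are not restored.

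The cost is a few table rows from values already collected and one or two sentences of SAP text. The suppression definition does not change. The downside is imprecise figures in 8 or fewer children, which must be labelled descriptive. Any change score will also carry some regression to the mean, because entry requires a Screening value above 18.
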